## CHARACTERISTICS OF THE STUDY POPULATION

### 1. Target Population

Three hundred ten adult male and female smokers 18 years of age or older who have been diagnosed with HIV/AIDS (identified through the UPENN CFAR Clinical Core, UPHS PennChart reviews and community-based HIV/AIDS organizations and events) and smoke at least 5 cigarettes per day will complete the study.

At PENN, a previous nicotine patch trial recruited a sample comprised of 45% women and 16% racial/ethnic minorities ([name] et al., 2010b). A separate PENN smoking cessation trial that used targeted efforts to recruit minority smokers had a sample comprised of 55% women and 52% racial/ethnic minorities ([name] et al., 2011). The UPENN CFAR Clinical Core population is 78% African American and 4% Hispanic American.

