## **2. Statistical Analysis**

### **Power**

Power is provided for the primary aims since the exploratory aim is hypothesis generating. Power calculations were all approximated as t- or z-tests (2-sided,  $\alpha = .05$ ), and conducted using PASS Software (Power and Sample Size, NCSS Software, Kaysville, UT).

Aim 1: The primary analysis is a comparison in week 12 and 24 cotinine-confirmed 7-day point prevalence quit rates between placebo and varenicline. For the week 12 comparison, we based our sample size selection on the expectation that quit rates in the placebo and varenicline arms would approximate those reported in past varenicline trials with the general population of smokers (i.e., placebo = 21.2%; varenicline = 50.3%; Gonzales et al., 2006). With a sample of 310, we have >90% power to detect a significant effect between our treatment arm. Notably, we have 80% to detect a difference in week 12 quit rates if the difference between treatment arms is as small as 15%, not 29% as found in Gonzales et al. (2006), since the effect for varenicline may be smaller in this sub-group of smokers. For the week 24 comparison, we based our sample size on the expectation that the quit rate in the placebo arm would be 14.5%, vs. 33.5% for varenicline (Gonzales et al., 2006). In this case, we have 85% power to detect a significant difference between treatment arms. However, we have 80% power to detect a difference between treatment arms if the treatment arm difference is only 15%, not the 19% reported in Gonzales et al. (2006), since the effect for varenicline may be smaller in this sub-group of smokers. Even though it may appear that we are over-powered for Aim 1, we require the proposed sample to conduct the non-inferiority analyses for Aim 2.

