Aim 2: The analyses are a comparison in week 12 and 24 differences in QOL and severe side effects. For QOL, the overall scale mean among HIV/AIDS patients is 58.3 (SD = 24.5, Range 14-100; Holmes & Shea, 1998). We have 80% power to detect a mean difference of 7.8 at any time-point between the treatment arms with the proposed sample of 310. For side effects, the analyses will involve a test of non-inferiority since we cannot use standard statistical tests and conclude that a non-significant comparison shows that the drug is safe (i.e., "the absence of evidence is not evidence of absence"). In our past study with varenicline, 61% of participants on varenicline reported no severe side effects, vs. 76% of participants on placebo, a 15% difference (Patterson et al., 2009). With the present sample size, we will have 80% power to detect similar equivalence between treatment arms in terms of the frequency of severe side effects over the course of the 12-week treatment, given that side effects are actually non-significantly different across the treatment arms.

Aim 3: The analyses will assess changes in affect and cognitive function as mediators of treatment arm effects at week 12 and 24. These measures are continuous difference scores. Our sample of 310 is well above the minimum sample of 200 recommended for models of this size (Haduk, 1987; Boosma & Gabrielli, 1985). The mediation hypothesis will examine the proportion of treatment effect explained (Lin et al., 1997; Vittinghoff et al., 2009), and will test each mediation hypothesis with a z-score generated using the delta method. Our sample of 310 gives us 80% power to observe small effects in a 1-sample test ( $\delta=0.20$ ) when testing at  $\alpha=0.05$ . There are four proposed mediating pathways (2 measures of affect and cognition, respectively) between treatment and outcome, so our type-1 error will be corrected to 0.0125. Our sample of 310 gives us 80% power to detect small to medium effects ( $\delta=0.19$ ) for changes in the proposed mediators, which we have seen in previous trials (Patterson et al., 2009; [name] et al., 2010a).

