### **Data Analysis**

[name] will oversee analyses which will be conducted using Stata, SAS, or R-Language software. Preliminary analyses will assess sample characteristics by treatment with chi-square or logistic regression (e.g., gender, dependence, depression). These variables will also be examined for their relationship to completion of outcome assessments. Variables related to treatment arm or completion of follow-ups will be included as covariates in analyses of study aims. Compliance measures will be evaluated across treatment arms, and controlled for in primary analyses. We will examine the correlation between self-report and pill count data and week 3 and 12 varenicline levels. Although we will use intent-to-treat as the primary method for

[figure not shown]
evaluating study aims, we will conduct a completers only analysis of study aims and examine study aims with participants lost to follow-up due to death excluded as done previously ([name] et al., 2003).

**Missing Data:** We will examine if the rate of missing data, primarily our smoking cessation outcome data, is related to a range of potential variables, including treatment arm allocation and HIV/AIDS-related, demographic, and smoking-related variables. Standard statistical methods will be used to identify possible correlates of missing data such as chi-square and regression. Variables found to be associated with the rate of missing data ( $p < .05$ ) will be included as covariates in the analyses of aims. In the event of items missing at random on measures, items will be imputed prior to calculating final scores using conditional means, estimated with an iterated version of Buck's method (Gleason & Staelin, 1975). Dropout and missed sessions present a more serious issue. The best way to deal with this is to avoid the problem in the first place by keeping subjects connected to the trial and motivated to complete measures. In our clinical trials, compliance and retention rates were >80% thanks to our close monitoring of participants and use of incentives to offset travel costs ([name] et al., 2008). Primary analyses will assume that all subjects for whom smoking outcome data are unavailable are smokers (intent-to-treat). This assumption, which is conventional in smoking cessation research, can attenuate the differences between study groups in quit rates. Thus, we will also conduct a "completers-only" analysis.

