**Aim 2: Assess effects of varenicline therapy on QOL and side effects.** Repeated-measures MANOVA will examine differences across treatment arms in QOL (total scale score and subscale scores) over the trial. Participant covariates will be included, such as medical treatment history. In addition, we will compare treatment arms in terms of the frequency of severe side effects (*individual, including cardiovascular side effects, and total*). Using logistic regression, we will test against the lower boundary on percent reporting only mild-moderate (i.e., < severe) side effects. The hypothesis test for equivalence is a test of whether the OR is out of the prescribed range for the difference between the treatment arms. This approach provides a more valid test of the potential safety of varenicline for individuals with HIV/AIDS vs. a simple comparison of mean responses on a side effects measure. *We will also examine if participants on tenofovir (vs. other HAART) experience a greater frequency or more severe varenicline side effects by including type of HAART as a covariate in these analyses and, if so, we can explore if this relationship is mediated by varenicline plasma levels using a regression-based path model. Lastly, we will also examine if the frequency of cardiovascular side effects is different between treatment arms while considering if participants are currently taking HAART or not by including a covariate for current HAART use in the logistic regression models of side effects.*

**Aim 3: Assess changes in affect and cognitive impairment as mediators of varenicline therapy's effect on quit rates.** We will use a regression-based path model approach to examine mediation of treatment effects based on MacKinnon et al. (2007). All variables will be standardized for the analyses. Candidate mediators include positive and negative affect and two cognitive performance task measures. Suspected mediators will be entered as standardized pre-post differences, continuously distributed and treated as normal in linear regression. The effects of treatment arm on mediators, and of mediators on outcome, will be assessed using linear regression and standardized variables. We will focus on changes in

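### Quality of life is to be analysed by repeated-measures MANOVA with no rule for a missed visit and no statement of which visits enter, so the analysis would probably be complete-case despite the intent-to-treat principle

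*Combined protocol and SAP*

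**What the plan says.** - **Method.** Data Analysis, Aim 2: "Repeated-measures MANOVA will examine differences across treatment arms in QOL (total scale score and subscale scores) over the trial". Participant covariates, such as medical treatment history, are to be included.
- **Schedule.** Table 2 and the Quality of Life (QOL) section place HAT-QoL at every visit after Intake: Weeks 0, 1, 3, 5, 7, 9, 12, 18 and 24.
- **Time-points of interest.** Power, Aim 2: "The analyses are a comparison in week 12 and 24 differences in QOL and severe side effects".
- **Analysis principle.** Data Analysis makes intent-to-treat the primary method for the study aims. The same sentence adds a second analysis: "evaluating study aims, we will conduct a completers only analysis of study aims".
- **Missing items.** Missing Data: "In the event of items missing at random on measures, items will be imputed prior to calculating final scores using conditional means".
- **Missed visits.** Missing Data: "Dropout and missed sessions present a more serious issue". What follows is prevention through retention, then the rule that a missing smoking outcome counts as smoking. Correlates of missingness are to be added as covariates.
- **Sensitivity of the QOL comparison.** Power, Aim 2: "We have 80% power to detect a mean difference of 7.8 at any time-point between the treatment arms with the proposed sample of 310".

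**The concern.** Classical repeated-measures MANOVA needs a full set of responses from each participant. Someone with eight of nine QOL scores contributes nothing if all nine visits enter. The plan recognises that missed sessions are a harder problem than missing items, but every remedy it gives addresses something else.

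Two things are at stake. First, a result described as intent-to-treat could rest on a subset selected by attendance. If attendance is related to QOL differently in the two arms, the comparison could be biased. Second, the completers-only analysis is meant to supplement the main one. If the main analysis already uses complete cases, the two could nearly coincide and the second would check very little. The MANOVA set could even be the smaller: someone seen at Weeks 12 and 24 who missed Week 5 would be excluded if all visits enter.

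**Working it through.** **1. Does any provision supply a missed QOL visit?**

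| Provision | Where | What it does for a missed QOL visit |
|---|---|---|
| Conditional-mean imputation | Missing Data | Fills items before a measure is scored; missed sessions are treated separately |
| Missing counted as smoking | Accrual; Missing Data | Cannot be applied to a QOL score |
| Covariates for correlates of missingness | Missing Data | Does not restore a dropped participant |
| Retention efforts | Missing Data | Prevention only |
| Telephone completion | Outcome Assessments, note | Fewer missed visits; no rule for those that remain |
| Visit windows of one week either side (Weeks 3 to 24) | Table 2, note | As above |

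None does.

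**2. The plan's own figure.** Inputs: SD 24.5 and N = 310 (Power, Aim 2); two-sided 0.05 and a t- or z-test approximation (Power); half the sample on varenicline, so 155 per arm (Risk/Benefit Assessment).

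Detectable difference at 80% power = SD × √(2/n) × (1.960 + 0.8416)

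- n = 155 per arm: 24.5 × √(2/155) × 2.8016 = 7.80. The stated 7.8 reproduces, with all 310 analysed and no covariate adjustment.
- n = 124 per arm (80% of 310 is 248): 24.5 × √(2/124) × 2.8016 = 8.72.
- Power at 7.8 with 124 per arm: Φ(7.8 / (24.5 × √(2/124)) − 1.96) = Φ(0.547) = 0.71.

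These are single-time-point approximations, like the plan's own, and not the power of the MANOVA.

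**3. Participants kept by a complete-case analysis.** The Accrual section projects that at least 80% complete follow-up; I use the 80% bound. Assume that Week 0 is complete, that Week 24 is covered by the completion rate, and that each other included visit is missed independently with probability m. The documents give no value for m; 0%, 2% and 5% are my assumptions.

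Kept = 310 × 0.80 × (1 − m)^k, where k is the number of included visits other than Weeks 0 and 24.

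| Visits entered | k | m = 0% | m = 2% | m = 5% |
|---|---|---|---|---|
| Weeks 0, 12, 24 | 1 | 248 | 243 | 236 |
| All nine | 7 | 248 | 215 | 173 |

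**4. Clustered misses.** If misses concentrate in the same people, fewer participants are lost. With a beta-binomial model, mean 5% and an assumed within-person correlation of 0.2 (parameters 0.2 and 3.8), the chance of no miss in seven visits is the product of (3.8 + i)/(4 + i) for i = 0 to 6, which is 0.80. Then 248 × 0.80 ≈ 198 are kept, against 173 under independence.

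**The case against.** The strongest reply is that the plan nowhere prescribes complete-case deletion. That stands. Deletion is inferred from the classical form of the method. The plan leaves the software open (Stata, SAS or R) and does not say whether the multivariate response is visits, subscales or both. A reader might infer that the plan has chosen complete cases; the text supports only that it gives no rule and that the named method, run conventionally, leads there.

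A reader might also take the nine-visit losses as the expected result. They are the unfavourable end. The Power section points to Weeks 12 and 24, and on that reading few participants are lost beyond dropout. Telephone completion and the visit windows reduce misses, and clustering reduces the loss further.

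A third reply is that the power statement already declares its basis: "Power calculations were all approximated as t- or z-tests", at a single time-point, with 310. That largely stands. The missing qualification is that 7.8 allows for no attrition. Adjusting for the Week 0 score could recover it: 8.72 × √(1 − r²) = 7.80 when r is about 0.45, a correlation the documents do not give.

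What remains is that a named aim has no rule for a missed visit, and that the method chosen uses partly observed participants poorly.

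**Conclusion.** The point holds as a gap with a clearly better alternative. The absence of a rule is a matter of text. Complete-case analysis is its probable consequence, not a stated one. At the 80% completion bound the analysed set would be 248 with no intermittent misses, 236 to 243 with three visits entered, and 173 to 215 with nine, the last two ranges resting on assumed independent misses of 2% to 5% per visit.

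A reader might infer that the QOL comparison is biased or that the trial is underpowered. The documents support neither. Nothing in them shows that missed visits relate to QOL differently by arm, and nothing excludes it. The plan ties its sample size to the Aim 2 non-inferiority analysis of side effects, not to QOL. The primary abstinence analysis has its own missing-data rule and is untouched. This should be corrected, but it does not threaten the trial's main conclusion.

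**What to change.** Replace the MANOVA with a likelihood-based mixed model for repeated measures on all available post-baseline HAT-QoL scores.

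- **Terms:** arm, visit, arm-by-visit, Week 0 score, the participant covariates already planned for Aim 2, and the correlates of missingness already planned under Missing Data.
- **Covariance:** unstructured, with a simpler fallback stated in advance, since eight post-baseline visits need 8 × 9 / 2 = 36 parameters.
- **Estimates:** name the Week 12 and Week 24 total-score contrasts as the Aim 2 QOL results, with subscales secondary.
- **Rules to state:** how a missing Week 0 score is handled, and how deaths are handled, consistent with the analysis already planned that excludes participants lost to death.
- **Sensitivity:** one missing-not-at-random analysis, for example multiple imputation with imputed scores shifted down in steps, separately by arm, reporting the shift at which the conclusion changes. A range of 0 to 12 points (about half the SD, 24.5 / 2 = 12.25) would serve as illustration, with no clinical meaning claimed.
- **Reporting:** the number in each arm with no post-baseline score.
- **Optional:** note that 7.8 assumes all 310 analysed without adjustment, and is about 8.7 at the 80% bound.

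The cost is SAP wording and code. The data are already scheduled, and Aim 1 already uses mixed-effects models. The downside is that the model relies on missing at random, and participants with no post-baseline score contribute only to the sensitivity analysis.

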### **Quality of Life (QOL)**

The HIV/AIDS-Targeted Quality of Life scale (HAT-QoL; Holmes & Shea, 1998; 1999) measures overall functioning, which will be the primary measure of QOL for this study, but several subscales of QOL are also included such as life satisfaction, health worries, HIV mastery, financial worries, and disclosure worries which will be explored in Aim 2 analyses. This measure will be administered at each visit after the Intake Session.

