**6. Risk/Benefit Assessment**

There is minimal risk for serious adverse events. The treatments and procedures used in this study have been shown to be relatively safe. Varenicline has also been studied in several clinical trials and shown to be safe and efficacious. Nevertheless, there are risks in participating in this trial, which are described above.

However, the risks of participating in this trial are offset by the potential benefits for participants and society. Participants who enroll in this trial will benefit from the knowledge that they are contributing in an important way to potentially furthering scientific knowledge concerning ways to improve treatment for smokers with HIV/AIDS. All smokers will receive behavioral counseling for smoking cessation. Half of the sample will receive varenicline. The trial results may support the use of varenicline for the treatment of nicotine dependence among those with HIV/AIDS, thereby reducing tobacco-related morbidity and mortality in this population.

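### Aim 2 powers a Week 12 and Week 24 quality-of-life comparison, but the planned MANOVA names no tested effect, no Week 12 or 24 contrast and no role for the Week 0 score

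*Combined protocol and SAP*

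**What the plan says.** All places are in the combined protocol and SAP.

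- **Power, Aim 2** describes the target: "The analyses are a comparison in week 12 and 24 differences in QOL and severe side effects". For QOL it gives the scale's distribution, "the overall scale mean among HIV/AIDS patients is 58.3 (SD = 24.5, Range 14-100", and states: "We have 80% power to detect a mean difference of 7.8 at any time-point between the treatment arms with the proposed sample of 310".
- **Power**, opening paragraph, gives the basis of every calculation: "Power calculations were all approximated as t- or z-tests (2-sided", at alpha 0.05.
- **Data Analysis, Aim 2** gives the method: "Repeated-measures MANOVA will examine differences across treatment arms in QOL (total scale score and subscale scores) over the trial". It adds participant covariates and offers medical treatment history as the example.
- **Quality of Life (QOL)** says of HAT-QoL: "This measure will be administered at each visit after the Intake Session". Table 2 accordingly marks it at Weeks 0, 1, 3, 5, 7, 9, 12, 18 and 24, which is nine visits.
- **Behavioral Counseling** has study medication start at the Week 0 session or directly after it. **Mid-treatment Assessments** places that visit's assessments before counseling. The Week 0 score is therefore in effect a pre-dose baseline.

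**The concern.** The test that was powered and the test that is planned are not the same. The power figure belongs to a two-arm comparison at one visit. A repeated-measures MANOVA across visits usually gives an arm main effect, which averages over visits, and an arm-by-time effect, which is an omnibus test over all within-person contrasts. The plan does not say which of these decides the QOL hypothesis, and neither one is the Week 12 or Week 24 difference. The hypothesis is directional (higher QOL on varenicline), and a significant omnibus arm-by-time result shows neither the direction nor the size of a difference at a given week.

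The plan also gives no role to the Week 0 score of the same scale. Elsewhere it is more specific: Aim 1 names its arm term and its time-by-arm interaction, and Aim 3 uses pre-post differences. QOL is the benefit hypothesis in Aim 2. What is at stake is a choice of test left open until the data are seen, and precision forgone from a baseline that is already being collected.

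**Working it through.** **Inputs from the document.** SD 24.5; difference 7.8; N = 310; two-sided alpha 0.05; equal allocation ("Half of the sample will receive varenicline"), so 155 per arm; nine QOL visits.

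**Assumed, not in the document.** The correlation ρ between HAT-QoL scores at different visits, ranged over 0.4, 0.5, 0.6 and 0.7; equal correlation between all visits (compound symmetry); no missing data.

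**Step 1: the plan's own figure.** SE = 24.5 × √(2/155) = 2.783. Power = Φ(7.8/2.783 − 1.96) = Φ(0.843) = 80.0% (79.8% by the t distribution). The detectable difference is (1.960 + 0.842) × 2.783 = 7.80. The stated figure reproduces, as a single-visit test without baseline adjustment.

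**Step 2: arm main effect over nine visits, Week 0 included.** SE = 24.5 × √[(1 + 8ρ)/9 × 2/155], which is 1.901, 2.074, 2.234 and 2.383 at the four correlations. If 7.8 points are present at all eight post-baseline visits, the averaged effect is 7.8 × 8/9 = 6.93. If they are present only at Weeks 12, 18 and 24, it is 7.8 × 3/9 = 2.60. Power = Φ(effect/SE − 1.96).

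**Step 3: arm-by-time test.** This is Hotelling's test on 8 contrasts: noncentral F with 8 and 301 degrees of freedom. Under compound symmetry the noncentrality is (155/2) × SS / [24.5² × (1 − ρ)], where SS is the sum of squared deviations of the nine visit effects from their mean. SS is 54.08 for the constant effect and 121.68 for the Weeks 12–24 effect. At ρ = 0.5 the noncentrality is 13.96 and 31.42.

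**Step 4: one visit, adjusted for Week 0.** Residual SD = 24.5 × √(1 − ρ²) = 22.46, 21.22, 19.60 and 17.50, used in the Step 1 formulas.

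| | ρ = 0.4 | 0.5 | 0.6 | 0.7 |
|---|---|---|---|---|
| Arm main effect, 7.8 constant after Week 0 | 95.4% | 91.7% | 87.4% | 82.9% |
| Arm main effect, 7.8 at Weeks 12–24 only | 27.7% | 24.0% | 21.3% | 19.2% |
| Arm-by-time, 7.8 constant after Week 0 | 65.5% | 75.1% | 85.6% | 94.9% |
| Arm-by-time, 7.8 at Weeks 12–24 only | 97.2% | 99.1% | 99.8% | >99.9% |
| Single visit, unadjusted (as in the plan) | 80.0% | 80.0% | 80.0% | 80.0% |
| Single visit, adjusted for Week 0 | 86.4% | 89.9% | 93.9% | 97.5% |
| Detectable difference, adjusted (unadjusted 7.80) | 7.15 | 6.75 | 6.24 | 5.57 |

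The total N that gives 80% power at 7.8 points with adjustment is 262, 234, 200 and 158, against 310 without.

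**The case against.** The case on the other side is substantial.

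- **The text does not put Week 0 among the outcomes.** A reader might infer that it does, because the analysis runs across the trial and the scale is given at nine visits. That is the likely reading, but the plan lists no visits for the model. Steps 2 and 3 therefore hold only if it is what is meant.
- **The covariate list is open.** Medical treatment history is given as an example, so baseline QOL is unnamed but not excluded. It would go too far to say that the plan rejects baseline adjustment.
- **The MANOVA is not generally weak.** A reader might infer from the 19% to 28% figures that it would miss a 7.8-point effect. The other cells of the table do not support that: for each time pattern and each correlation, at least one of the two tests exceeds 80%. For a constant effect at ρ = 0.4 and 0.5, the nine-visit main effect (95.4%, 91.7%) beats the adjusted single-visit test (86.4%, 89.9%), because it averages many visits. The arm-by-time test also uses Week 0, as a within-person reference.
- **The gain from adjustment has no fixed size.** It depends on a correlation that the document does not give.

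All four points stand. They do not remove the mismatch between the two sections. Each test does worst under the time pattern where the other does best, so leaving the deciding test unnamed allows the choice to follow the data. Whichever test is read, the Week 12 and Week 24 differences are still not estimated.

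**Conclusion.** The concern holds as a mismatch between the powered and the planned comparison, together with a free improvement left unused. The mismatch is read directly from the two sections and needs no assumed correlation. The figures do rest on assumptions: ρ between 0.4 and 0.7, compound symmetry, all 310 participants observed and, for the MANOVA rows, Week 0 as one of nine outcomes. Within that range the planned analysis could have anything from about 19% to over 99% power for a 7.8-point effect, depending on the test and on when the effect appears. A Week 12 or Week 24 contrast adjusted for Week 0 has 86.4% to 97.5% whether the effect is constant or late, provided it is present at that week.

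A reader might also infer that the stated 80% is wrong. It is not: it reproduces exactly for the test it describes, which makes no use of baseline. The plan forgoes a gain; it does not misstate its power. QOL is an Aim 2 outcome, so none of this touches the primary abstinence comparison.

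**What to change.** In Data Analysis, Aim 2:

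1. Analyse post-baseline HAT-QoL by ANCOVA or a linear mixed model, with the Week 0 score of the same scale or subscale as a covariate.
2. Keep Week 0 out of the outcome vector.
3. Name the arm difference at Week 12 and at Week 24 as the contrasts to be estimated, each with a 95% confidence interval. If an omnibus test across visits is kept, label it supportive.

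In Power, Aim 2, the 7.8-point figure can stay. A baseline-adjusted detectable difference may be added beside it, with its assumed correlation stated.

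The cost is wording only, agreed before the arms are unblinded for analysis. It needs no new visits, measurements or participants.

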**PROTOCOL ABSTRACT**

Among people diagnosed with HIV/AIDS, the widespread use of highly active antiretroviral therapy (HAART) has greatly improved survival rates (Palella et al., 1998) and changed the leading causes of death, from AIDS-related diseases (e.g., non-Hodgkin's lymphoma, Kaposi sarcoma), to cardiovascular disease and lung cancer (Palella et al., 2006). As such, addressing modifiable risk factors for disease mortality among those with HIV/AIDS, including tobacco use, has become a critical priority (Nahvi & Cooperman, 2009). To date, only three smoking cessation clinical trials have been conducted with those with HIV/AIDS (Lloyd-Richardson et al., 2009; Vidrine et al., 2006; Ingersoll et al., 2007) none of which investigated the efficacy of FDA-approved medications for nicotine dependence. Varenicline is an  $\alpha 4\beta 2$  nicotinic acetylcholine receptor partial agonist with greater efficacy for treating nicotine dependence than bupropion (Gonzales et al., 2006; Jorenby et al., 2006) or nicotine patch (Aubin et al., 2008; Biazzo et al., 2010; Stapleton et al., 2008). Varenicline may be particularly efficacious for treating nicotine dependence among individuals with HIV/AIDS given that depression symptoms (Cruess et al., 2003) and cognitive impairment (Lindl et al., 2010) are common in this population, increase during smoking abstinence and predict smoking relapse (Zvolensky et al., 2009; Evans & Drobis, 2009), and are significantly reduced by varenicline (Patterson et al., 2009; Smith et al., 2009; Philip et al., 2009; Rollema et al., 2009). Therefore, we will conduct a randomized, double-blind, placebo-controlled trial of varenicline with smokers with HIV/AIDS. Specifically, 310 smokers with HIV/AIDS will be randomized to varenicline plus 9 weeks of smoking cessation counseling or placebo plus 9 weeks of smoking cessation counseling. The primary outcome variable for this study will be 7-day biochemically confirmed tobacco

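### The Aim 2 non-inferiority test has rates and power for total severe side effects only; if it is carried over to rare individual or cardiovascular effects it is uninformative or falsely reassuring

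*Combined protocol and SAP*

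**What the plan says.** The Power section, Aim 2, states: "For side effects, the analyses will involve a test of non-inferiority". It cites one earlier study, in which "61% of participants on varenicline reported no severe side effects, vs. 76% of participants on placebo, a 15% difference", and then claims that "we will have 80% power to detect similar equivalence between treatment arms in terms of the frequency of severe side effects" over the 12-week treatment period. These figures all describe participants with no severe effect of any kind, that is, the total.

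The Data Analysis section, Aim 2, compares the arms on the frequency of severe side effects, "individual, including cardiovascular side effects, and total". It goes on to describe a logistic regression tested against a lower boundary on the percentage of participants whose effects stayed below severe, and defines the equivalence test as "a test of whether the OR is out of the prescribed range for the difference between the treatment arms". Neither the boundary nor the range is given as a number. No limit, expected rate or power is given for any individual or cardiovascular effect.

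The same paragraph ends with a separate logistic regression asking whether cardiovascular side effects differ in frequency between arms, with current HAART use as a covariate. The Potential Study Risks section describes the cardiac and vascular risks as rare, without a figure.

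**The concern.** A limit suited to an event seen in 24% to 39% of participants does not transfer to one seen in a few percent. On the risk-difference scale, 15 points is many times the base rate of a rare event, so a large relative excess fits inside it. On the odds-ratio scale, a limit near 2 needs far more events than 155 per arm can supply, so the test fails even when the arms are identical.

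The Background says the safety of these medications in people with HIV/AIDS is unknown, and the Data Analysis section presents this method as a more valid test of safety than a simple comparison. A cardiovascular result labelled non-inferior, or not shown non-inferior, would be read in that light although the procedure could not support either message. Because the plan mentions both a percentage boundary and an odds-ratio range, the scale could also be chosen after the data are seen.

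**Working it through.** **Inputs.**
- Sample: "310 smokers with HIV/AIDS will be randomized to varenicline plus 9 weeks of smoking cessation counseling or placebo", and "Half of the sample will receive varenicline" (Risk/Benefit Assessment), so 155 per arm.
- Error rate: "Power calculations were all approximated as t- or z-tests", two-sided 0.05. No separate level is given for non-inferiority, so one-sided 0.025 is used.
- Rates behind any limit: severe effects in 100 − 76 = 24% on placebo and 100 − 61 = 39% on varenicline.
- Severe cardiovascular rate: not in the documents. Placebo rates of 1% to 5% are assumed.

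**Implied limits.** Risk difference: 39 − 24 = 15 points. Odds ratio: (0.39/0.61)/(0.24/0.76) = 0.639/0.316 = 2.02; log 2.0246 = 0.705.

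**The plan's own 80%, for the total.** With no true difference, power = Φ(0.15/√(2p(1−p)/155) − 1.96), where p is the common proportion free of severe effects.
- p = 0.685 (midpoint of 61% and 76%): SE = 0.0528, power = 81%.
- p = 0.76: SE = 0.0485, power = 87%.
- p = 0.61: SE = 0.0554, power = 77%.

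On the odds-ratio scale, Φ(0.705/√(2/(155p(1−p))) − 1.96) gives 82% at 0.685 and 76% at 0.76. The stated 80% is reasonable for the total.

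**Odds-ratio limit 2.02, equal true rates.** Exact binomial enumeration at 155 per arm, with the upper 95% limit on the log odds ratio. The range reflects zero cells counted as not met versus a 0.5 correction.

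| True rate in both arms | Trials meeting the limit |
|---|---|
| 1% | 0.9–1.7% |
| 2% | 8–11% |
| 3% | 17–19% |
| 5% | 27% |
| 10% | 45–47% |

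A hand check: with equal counts k per arm, the upper limit is exp(1.96 × √(2/k + 2/(155−k))). For k = 3 this is 5.03 and for k = 8 it is 2.74, so identical counts fail. At k = 17 it is 2.04 and at k = 18 it is 2.00, so each arm needs at least 18 events (11.6%) to pass.

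The sample per arm for 80% power is 2/(p(1−p)) × ((1.96 + 0.84)/0.705)²: about 3,187 at 1%, 1,610 at 2% and 665 at 5%.

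**15-point limit, true excess on varenicline.** Exact enumeration with the Newcombe upper 95% limit compared with 0.15.

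| Placebo vs varenicline | Ratio | Trials passing |
|---|---|---|
| 1% vs 5% | 5 | 99.5% |
| 1% vs 8% | 8 | 84% |
| 2% vs 6% | 3 | 99% |
| 2% vs 8% | 4 | 89% |
| 2% vs 10% | 5 | 65% |
| 3% vs 9% | 3 | 86% |
| 3% vs 12% | 4 | 47% |
| 5% vs 10% | 2 | 88% |
| 5% vs 15% | 3 | 30% |

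**One possible data set.** With 3/155 on placebo and 12/155 on varenicline, the odds ratio is (12 × 152)/(143 × 3) = 4.25, Fisher's p is 0.03, and the Newcombe interval for the excess is 1.0 to 11.3 points. These data are significantly worse and also inside a 15-point limit.

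**Sensitivity to the error rate.** At one-sided 0.05, the odds-ratio test with equal 2% rates is met in 16–19% of trials, and 2% vs 8% passes the 15-point limit in 94%. The conclusion is unchanged.

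**The case against.** The strongest reply is about scope. The plan says the arms will be compared on individual effects and the total, but the boundary sentence names a single participant-level quantity, the percentage with nothing worse than mild to moderate effects. That fits the total best and matches the study cited in the Power section. This stands: that each individual effect will be put through the test is an inference. It remains the natural one, because no other test is named for that comparison.

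Second, the limit and rates are not the plan's. The 15 points are a past observed difference, the prescribed range has no number, and rare describes cardiac and vascular risks in general, not self-reported severe checklist items. This also stands, and so the results are conditional and shown over a range.

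Third, a reader might infer that the trial is set to certify a several-fold cardiovascular excess as safe. The documents do not support that. The test is defined through the odds ratio, and with a limit of 2.02 a true 2% vs 8% passes in about 0.05% of trials. The false reassurance arises only if the percentage boundary is taken as 15 points. Even then, the planned cardiovascular comparison would often show the harm: with an unadjusted two-sided 5% chi-square test as a stand-in, the difference is significant in 71% of trials at 2% vs 8% and 90% at 1% vs 8%. Passing without a significant difference falls to 29% and 10%, though it is still 45% at 1% vs 5%. The DSMB also reviews safety data.

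Finally, failing to show non-inferiority is not a finding of harm, and some individual effects, such as nausea, may be common enough to test. Both points are fair. They argue for a fix aimed at effects with no stated limit or power, not for leaving the scope open.

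**Conclusion.** The concern holds as a problem of unclear scope with a real consequence. The rates and the 80% power support a non-inferiority test on the total only. Extended to rare effects, an odds-ratio limit taken from the total is close to uninformative: at placebo rates of 1% to 2%, identical arms meet it in roughly 1% to 11% of trials, and at 5% in 27%. Read as 15 points, the limit would pass about a 5- to 8-fold excess at 1%, a 3- to 4-fold excess at 2% and a 3-fold excess at 3% in 84% to 99.5% of trials. At 5%, only about a 2-fold excess passes reliably.

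This rests on 155 per arm, one-sided 0.025, a limit inferred from the total and assumed event rates. It does not affect the total, and the primary outcome is abstinence, so the weight is moderate.

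**What to change.** In the Data Analysis section, Aim 2, state that the non-inferiority test applies to the total only, that is, any severe side effect. For cardiovascular and other individual severe effects, report counts by arm and the risk difference with an exact or Newcombe 95% interval. Keep the planned HAART-adjusted cardiovascular comparison. State that no non-inferiority conclusion will be drawn for any effect that has no limit and power given in advance.

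The cost is a few sentences of plan text, with no new data, visits or participants. The trial gives up formal non-inferiority claims for individual effects. For rare ones it could not have supported them at this sample size.
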